3.1 STUDY OUTCOME MEASURES	15
4. PARTICIPANT ENTRY	15
4.1 RECRUITMENT	15
4.2 PRE-REGISTRATION EVALUATIONS	16
4.3 INCLUSION CRITERIA	16
4.4 EXCLUSION CRITERIA	16
4.5 WITHDRAWAL CRITERIA	16
5. ADVERSE EVENTS	16
5.1 DEFINITIONS	16
5.2 REPORTING PROCEDURES	17
5.3 RESPONSIBILITIES	18
6. ASSESSMENT AND FOLLOW-UP	19
7. STATISTICS AND DATA ANALYSIS	19
7.1 DESCRIPTION OF STATISTICAL METHODS	19
7.2 THE NUMBER OF PARTICIPANTS	20
7.3 THE LEVEL OF STATISTICAL SIGNIFICANCE	20
7.4 CRITERIA FOR THE TERMINATION OF THE TRIAL.	21
7.5 PROCEDURE FOR ACCOUNTING FOR MISSING, UNUSED, AND SPURIOUS DATA.	21
7.6 INCLUSION IN ANALYSIS	21
8. ARCHIVING	21
9. REGULATORY ISSUES	21
9.2 CONSENT	22
9.3 CONFIDENTIALITY	22
9.4 INDEMNITY	22
9.5 SPONSOR	22
9.6 FUNDING	22
9.7 MONITORING	22
10. STUDY MANAGEMENT	23
11. PUBLICATION POLICY	23
12. REFERENCES	23

GLOSSARY OF ABBREVIATIONS

AE	Adverse event
AR	Adverse reaction
CI	Chief Investigator
CRF	Case Report Form
CT	Clinical Trials
DMC	Data Monitoring Committee
GCP	Good Clinical Practice
GP	General Practitioner
ICF	Informed Consent Form
ICH	International Conference of Harmonisation
NHS	National Health Service
NRES	National Research Ethics Service
PI	Principal Investigator
PIS	Participant/ Patient Information Sheet
R&D	NHS Trust R&D Department
REC	Research Ethics Committee
SAE	Serious Adverse Event
SAR	Serious Adverse Reaction
SUSAR	Suspected Unexpected Serious Adverse Reaction
SmPC/SPC	Summary of Products Characteristics
SOP	Standard Operating Procedure
TMF	Trial Master File
TSG	Trials Steering Group

KEYWORDS

Corticosteroid
 Local anaesthetic
 Trigger finger
 De Quervains tenosynovitis
 Carpal tunnel syndrome

STUDY SUMMARY

TITLE	The SToICAL Study: The Soft Tissue Injection of Corticosteroid And Local anaesthetic Study – A single site non-inferiority randomised control trial evaluating pain after soft tissue corticosteroid injections with and without local anaesthetic
DESIGN	A single site, patient and assessor blinded, non-inferiority randomised control trial of patients with a clinical diagnosis of trigger finger, de Quervains tenosynovitis or carpal tunnel syndrome, treated with a corticosteroid injection co-administered with or without local anaesthetic.
AIMS	To determine whether pain experienced during the 24 hours after a corticosteroid injection to the hand and wrist is no worse than (not inferior to) the pain experienced after a corticosteroid and local anaesthetic injection.
OUTCOME MEASURES	
The primary objective;
 
Investigate whether there is a difference in pain VAS scores at 1-hour after a corticosteroid injection for trigger finger, de Quervains tenosynovitis or carpal tunnel syndrome co-administered with or without local anaesthetic.
 
The secondary objectives;
 
i) Investigate whether there is a difference in pain VAS scores during the 24-hours after a corticosteroid injection for trigger finger, de Quervains tenosynovitis or carpal tunnel syndrome co-administered with or without local anaesthetic.
 
ii) Investigate whether there is a difference in the pain VAS scores at the time of the corticosteroid injection for trigger finger, de Quervains tenosynovitis or carpal tunnel syndrome co-administered with or without local anaesthetic.
 
iii) Investigate the difference in the additional analgesia required and in the functional use of the hand during the first 3 hours following a corticosteroid injection for trigger finger, de Quervains tenosynovitis or carpal tunnel syndrome co-administered with or without local anaesthetic.
 
These outcomes will be determined by assessing patients' pain using a 100mm VAS score before and at time of the injection, and at 5-minutes, 1-hour, 2-hours, 3-hours and 24-hours after the injection. This will be supplemented by questions to determine whether additional analgesia was required and if there was any effect on hand function following the injection. No subgroup analysis will be performed.

POPULATION	Patients attending elective hand and wrist outpatient clinics at the University Hospitals Plymouth NHS Trust with a clinical diagnosis of trigger finger, de Quervains and carpal tunnel syndrome.
ELIGIBILITY	All patients over the age 18 years old with a clinical diagnosis of trigger finger, de Quervains tenosynovitis or carpal tunnel syndrome and who are able to give written informed consent for treatment will be included. Patients will be excluded if they have had previous surgery or corticosteroid injection for the condition being treated at the site considered for injection. A previous corticosteroid injection elsewhere in the hand does not exclude a patient from the trial. Those who are pregnant, breast-feeding or who have a history of hypersensitivity to corticosteroid or local anaesthetic will be excluded.
DURATION	The study will run for a 12-month period or until 100 patients have been recruited to the trial.

1. INTRODUCTION

1.1 BACKGROUND

Corticosteroid injections are used in the treatment of a variety of hand and wrist conditions. They have local anti-inflammatory effects from blocking cytokine production involved in the inflammation process¹. The injections can be administered intra or extra-articularly, with or without image guidance and with or without local anaesthetic. The co-administration of a local anaesthetic and corticosteroid aims to reduce pain soon after the injection. However no studies have directly compared this with using corticosteroid alone, to determine whether there is a difference in patients pain.

Conditions:

Trigger finger, de Quervains tenosynovitis and carpal tunnel syndrome are painful conditions of the hand and wrist where corticosteroid injections have a role in their treatment.

Trigger finger is a condition that causes locking on flexion of the involved finger, dysfunction and pain as a result of thickening of the first annular pulley, which affects 2% of the general population^{2, 3}. Available treatments are operative (A1 pulley release) and non-operative (corticosteroid injection and splinting). Operative treatment has an effective cure rate of 89-97% with increased costs, longer absence from work, and the possibility of surgical complications⁴. Corticosteroid injection is an effective and safe treatment with cure rates ranging from 60-92%³.

De Quervains tenosynovitis is a disorder that causes radial sided wrist pain as a result of mechanical impingement of the tendons within the first extensor compartment⁵. The prevalence of de Quervains tenosynovitis in the United Kingdom is 0.5% in men and 1.3% in women⁶. Available treatments are operative (slitting or removing a strip of the tendon sheath) and non-operative (corticosteroid injection and splinting). Operative treatment has an effective cure rate of 91%, but is more invasive and associated with higher costs and the possibility of surgical complications⁷. Corticosteroid injections have cure rate of 83% and is a superior treatment compared to splinting⁸.

Carpal tunnel syndrome causes pain and numbness in a median nerve distribution in the hand from compression of the nerve within the carpal tunnel, and affects 3.8% of the general population^{9, 10}. Available treatments are operative (Carpal tunnel decompression) and non-operative (corticosteroid injection and wrist splinting). Surgery is preferred in severe cases whereas in mild and moderate cases non-surgery treatments are used initially¹¹.

Administration:

Corticosteroid injections administered into soft tissue for these conditions can be performed under ultrasound guidance or by using anatomical landmarks. Landmark guided injections can be performed at the time of consultation within the outpatient clinic without additional imaging. Ultrasound guided injections are performed by the radiology department with variable on-the-day availability. Often a separate outpatient appointment is required to deliver this treatment. The accuracy and effectiveness of both methods of delivery have been studied.

A cadaveric study showed no statistical difference in the accuracy between ultrasound and landmark guided injections for de Quervains tenosynovitis or carpal tunnel syndrome. The incidence of success without ultrasound guidance was 95% and 100% for de Quervains tenosynovitis and carpal tunnel syndrome respectively; injections for trigger finger were not included¹². Despite both ultrasound and landmark guided injections being effective in reducing symptoms and improving hand function in carpal tunnel syndrome, ultrasound guided injections have shown superior clinical outcomes^{13,14}.

Although no clinical study directly compared ultrasound versus landmark guided corticosteroid injections for de Quervains tenosynovitis, there is evidence suggesting that ultrasound guidance has a slightly

better clinical outcome. A pooled quantitative literature evaluation of landmark-guided injections showed a complete resolution of symptoms in 83% of patients, compared to 92% in a study using ultrasound guidance^{8,15}. A prospective randomised trial showed no superior clinical benefit in administering corticosteroid injections for trigger finger with ultrasound guidance, and noted the extra time and effort required¹⁶. There is also no benefit to injecting the corticosteroid into the tendon sheath versus outside the sheath¹⁷.

Landmark guided corticosteroid injections for trigger finger, de Quervains tenosynovitis and carpal tunnel syndrome are performed routinely in clinical practice across the National Health Service (NHS). Evidence supports the efficacy for landmark guided injections, although in some conditions the use of ultrasound can slightly improve clinical outcomes. However, nowhere considers the additional costs, the delay in treatment and the patient experience benefits of receiving an on-the-day clinic based treatment.

The number of corticosteroid injections given at University Hospitals Plymouth NHS Trust in the elective hand and wrist clinic was determined using clinical codes. 25 patients over a 6-month period were coded to have had a corticosteroid injection. It is likely the coding system is not accurately capturing all corticosteroid injections performed. Anecdotally it is felt that 3-5 corticosteroid injections are performed each week. In light of this, a three week prospective audit was conducted during which 11 corticosteroid injections were performed, which is an average of 3.6 per week.

Corticosteroid injections:

There are a variety of injectable synthetic corticosteroids with different half-lives and variable duration of clinical benefit even between individuals with the same corticosteroid¹⁸. Triamcinolone (40mg/1ml) is used routinely for soft tissue corticosteroid injections of the hand and wrist at University Hospitals Plymouth NHS Trust by the local Hand and Wrist surgeons.

There are a number of possible adverse effects with corticosteroid injections, which include; local infection, skin atrophy, skin depigmentation, fat necrosis and allergic reactions¹⁹. It can increase blood glucose level in diabetic patients for up to 5 days, although a study of extra-articular injections in the hand and wrist showed that this was not clinically significant²⁰. The National Institute for Clinical Excellence (NICE) recommends that caution be used if the patient is taking oral anti-coagulation²¹, but it is not a contra-indication. Another possible adverse effect is a post injection flare, which is a local increase in inflammation that develops within hours and can last 2-3 days²². The post injection flare has been described in intra-articular injections to begin after 90 minutes, last for less than 24 hours and be as a result of a crystal-induced synovitis²³. It may then be 3 to 7 days before the corticosteroid becomes effective²⁴.

The Cochrane reviews for corticosteroid injection in trigger finger and de Quervains reported no adverse events^{2,5}. A review of over 9000 corticosteroid injections for carpal tunnel syndrome found; severe side effects in <0.1% (tendon rupture, intraneuronal injection, gangrene), minor persistent local effects in 2%, (subcutaneous atrophy, depigmentation) and transient effects in 15-20% (pain, bruising, facial flushing)²⁵.

Local anaesthetic:

Corticosteroids are often mixed with local anaesthetic and co-administered to reduce pain after the injection. 1ml of 1% lidocaine is often mixed with 1ml Triamcinolone (40mg/1ml) as part of routine practice for soft tissue corticosteroid injections in the hand and wrist at University Hospital NHS Trust by the local Hand and Wrist surgeons. The mixing does not create a greater propensity for corticosteroid crystals to aggregate or change size; therefore they are safe to co-administer²⁶.

Lidocaine is a local anaesthetic with a rapid onset of less than 2 minutes and its effects can last for 1 to 3 hours, and has a maximum dose of 5mg/kg²⁷. Lidocaine works by blocking voltage gated sodium channels in neuronal cell membranes preventing the propagation of action potentials. The British

National Formulary advises that local anaesthetic should not be injected into inflamed or infected tissues²⁸.

An injection containing lidocaine can be painful because of the acidity of the solution, which can be neutralised with sodium bicarbonate. However, a randomised control trial failed to demonstrate a statistically significant benefit of sodium bicarbonate in extra-articular corticosteroid injections with local anaesthetic in the hand and wrist²².

Assessment of pain:

Pain is subjective and multi-dimensional therefore it is difficult to fully evaluate the complete pain experience. The 100mm visual analogue scale (VAS) score is a widely used method for assessing pain. It is generally accepted that a pain VAS score of 30, 70 and 100 indicates the upper boundaries of mild, moderate and severe pain intensity²⁹.

A reduction in pain score does not directly correlate with an improvement in a patients' experience of that pain. Minimally clinically important difference (MCID) is what minimal change in a pain VAS score would indicate a real change in a patients' pain intensity. A systematic review of 29 studies identified an absolute MCID ranging from 8mm to 40mm and could not conclude a single MCID value because of the variety of different methods used to calculate the MCID. The importance of making a comparison against a patients' baseline pain was recognised³⁰.

The authors are not aware of any studies that have evaluated the MCID in pain VAS score following soft tissue corticosteroid injection in the hand and wrist. A recent observational study assessed MCID in VAS score in 224 post-operative patients concluded a MCID in pain VAS score of 10mm³¹. Two different papers determine 14mm as the MCID in pain VAS score in treatment of rotator cuff disease and following shoulder arthroplasty^{32, 33}. A large prospective multicentre study determined the MCID in pain VAS score in those with knee osteoarthritis to be 19.9mm³⁴. This study was reference and a MCID of 20mm used to evaluate patient reported outcomes following arthroplasty surgery³⁵. A 20mm MCID has also been used in other studies evaluating post procedural pain³⁶, one of which was also investigating pain following soft tissue corticosteroid injections in the hand²². Therefore, for the purpose of this study a MCID of 20mm will be used.

Non-inferiority studies:

Non-inferiority studies are a one-sided test used to determine if a novel treatment is no worse than the standard treatment. It is designed to show that the novel treatment is no less than a pre-specified unimportant amount from the standard intervention. Equivalence studies are a two-sided test used to show a novel treatment is no worse or no better than the standard treatment. It is designed to show that the two treatments do not differ in either direction by more than a pre-specified unimportant amount. This pre-specific unimportant amount is the margin that defines the "zone of indifference" within which the interventions are considered equivalent or non-inferior. Non-inferiority studies are often used in therapeutic trials when a novel treatment offers additional benefits to the standard treatment and the aim is to show that is non-inferior^{37,38}.

In this instance the standard treatment is considered as a corticosteroid co-administered with local anaesthetic and the novel treatment corticosteroid alone. The hypothesis is that the pain at 1-hour post injection of corticosteroid alone is no worse than (not inferior to) the pain following a corticosteroid injection co-administered with local anaesthetic. The benefits of injecting corticosteroid alone, if the post injection pain was not inferior to co-administering it with local anaesthetic includes; stopping unnecessary administration of medication and reducing treatment time and cost. The zone of indifference has been set at <20mm, which has been determined from a MCID of 20mm a value below which it has been shown that there is no difference in pain experienced by the patient.

1.2 RATIONALE FOR CURRENT STUDY

Study: The SToICAL Study

The authors are not aware that a study exists that assesses pain following soft tissue corticosteroid injections in the hand and wrist, co-administered with and without local anaesthetic. Although, corticosteroids and local anaesthetic are often co-administered no evidence is currently available to support this.

The effects of the local anaesthetic only last for 2-3 hours; therefore it would not provide relief from post-procedure flares nor bridge the time until the corticosteroid becomes effective. Administering local anaesthetic can be painful because of the acidity of the solution and means higher volume injections are given. The use of local anaesthetic may also worsen paraesthesia symptoms or result in paraesthesia in parts of the hand, preventing normal function for the duration of its action.

Adding local anaesthetic increases the cost, time and clinical waste of the treatment. Although, the additional cost per treatment may not be significant when considering the number performed across the National Health Service, the saving may be considerable.

We hypothesise, that the pain experienced at 1-hour after a corticosteroid injection for trigger finger, de Quervains tenosynovitis and carpal tunnel syndrome is no worse than when the corticosteroid is co-administered with local anaesthetic.

1.3 PATIENT AND PUBLIC INVOLVEMENT

This study proposal was discussed with a number of patients within the hand clinic. To collect objective evidence a patient opinion questionnaire was developed.

13 patients completed this questionnaire of which 10 had had previous corticosteroid injections (9 for trigger finger and 1 for carpal tunnel syndrome). 7 were given the injection with local anaesthetic, 1 without local aesthetic and 1 did not know if local anaesthetic was used or not. All 13 patients indicated that they would be able to complete and return the proposed patient assessment form and if asked would agree to be randomised into this study.

When asked about their thoughts about being included in a study like this, patients responded:

“Not a problem”

“I would be willing to help the study”

“Great study as could be wasting money”

“No problem whatsoever”

“I’ll be happy if it can help doctors with patients’ treatment”

When asked what would put them off about being included the majority said “nothing”, however 2 patients who had had injections before were reluctant to have further injections because they were painful and not well tolerated.

2. STUDY OBJECTIVES

The primary objective:

Investigate whether there is a difference in pain VAS scores at 1-hour after a corticosteroid injection for trigger finger, de Quervains tenosynovitis or carpal tunnel syndrome co-administered with or without local anaesthetic.

The secondary objectives:

i) Investigate whether there is a difference in pain VAS scores during the 24-hours after a corticosteroid injection for trigger finger, de Quervains tenosynovitis or carpal tunnel syndrome co-administered with or without local anaesthetic.

ii) Investigate whether there is a difference in the pain VAS scores at the time of the corticosteroid injection for trigger finger, de Quervains tenosynovitis or carpal tunnel syndrome co-administered with or without local anaesthetic.

[figure not shown]
iii) Investigate the difference in the additional analgesia required and in the functional use of the hand during the first 3 hours following a corticosteroid injection for trigger finger, de Quervains tenosynovitis or carpal tunnel syndrome co-administered with or without local anaesthetic.

3. STUDY DESIGN

This is a single site, patient and assessor blinded, non-inferiority randomised control trial where patients will be randomised to receive an injection of corticosteroid alone or an injection of corticosteroid co-administered with local anaesthetic to treat; trigger finger, de Quervains tenosynovitis or carpal tunnel syndrome.

The reviewing physician will identify eligible patients during 20-minute outpatient hand and wrist clinic appointments. Providing that the patient meets the inclusion and exclusion criteria the supernumerary registrar in clinic will explain the study to the patient and provide them with an information leaflet (Appendix 1). Patients considering enrolment will return to the waiting room to read the study information. This allows sufficient time for the patients to go through the information at their own pace and for the clinic to continue to avoid it running behind. The patients can have the duration of the morning clinic (if required) to consider enrolment in the study. After the patients have read the study information they will return to clinic as soon as they are ready and be seen by the registrar a separate clinic room. There will be no pressure to participate and if patients do not want to be included they will still receive treatment within the clinic, as they would do normally.

Normal practice for patients attending outpatient hand and wrist clinic with a clinical diagnosis of trigger finger, de Quervains tenosynovitis or carpal tunnel syndrome:

Once the patient feels well informed and comfortable to participate, consent will be received (Appendix 2) and a patient participation record completed (Appendix 3). A photocopy of the consent form will be given to the patient and another copy kept in the patients' hospital notes. The original consent form will be kept in the site file along with the patients' participation record. The patient participation record contains a patient participation number, which is the only link between the patient and the treatment

delivered. The supernumerary registrar uses a computerised randomisation system to randomise the patient into one of the two treatment arms, whilst the patient completes the pre-injection validated pain VAS score on the patient assessment record (Appendix 4).

Patients will be randomised using the simple randomisation service provided by Sealed Envelope Ltd. This is an online service that provides random permuted block randomisation, ensuring participants are balanced between the control and treatment group. The physician will use a unique URL and password to randomise patients in A (treatment) or B (control) group.

Patients will receive injections containing one of the two following solutions, delivered under landmarks guidance to treat either; trigger finger, de Quervains tenosynovitis or carpal tunnel. Both combinations are used as part of routine practice for soft tissue corticosteroid injections in the hand and wrist at University Hospital NHS Trust by the local Hand and Wrist surgeons:

- A. 1ml of triamcinolone (40mg/1ml)
- or
- B. 1ml of triamcinolone (40mg/1ml) + 1ml 1% Lidocaine

The registrar will draw up, prepare the treatment in a separate room so that the patient will remain blinded. Neither treatment can be distinguished from one another by their appearance alone.

During the clinic appointment the patient will complete a pain VAS score prior to the injection, for pain experience at the time of the injection and at 5 minutes post injection on the patient assessment record. The pain VAS score of the pain experience during the corticosteroid steroid will be recorded immediately after the procedure. The patient then takes the patient assessment record home to complete further pain VAS scores at; 1-hour, 2-hour, 3-hour and 24-hours following the injection. The timings at which these scores must be recorded will be clearly documented on the patient assessment record by the physician before leaving clinic to help remind the patient. There are three further questions, on the same form; that the patient will be required to answer at 3-hours post injection (Appendix 4).

During the first 3-hours after your steroid injection:

1. Did you take any additional painkillers because of pain at the injection site?

YES Medication: _____

Time taken: _____

NO (go to next question)

2. Did you have any reduction in hand function, below normal, as a result of the injection?

YES please describe your reduction in function:

NO

3. Did you experience any new numbness in your hand, as a result of the injection?

YES

NO

After the final pain VAS score at 24-hours the patient will receive a follow-up call by the registrar to ensure the assessment form has been completed, to answer any questions and remind the patient to

[figure not shown]
return the form using the prepaid envelope provided. After the form is posted the patients participation in the study will be complete.

The routine dictated clinic letter completed by the physician will outline the patients diagnosis, inclusion into the trial, and an overview of the trial and the consent process, but will not specify which treatment was delivered. A copy of this letter is kept in the patients' notes and a copy is sent to the GP.

The patient participation record and a copy of the consent form will be kept in the site file and stored in a locked filling cabinet in [name], Level 11, Derriford Hospital.

Returned patient assessment records will be collected by the departmental secretary, held within the site file and remain sealed until the end of recruitment. Once the recruitment phase is completed the patient assessment records will be open and the pain VAS scores will be measured, recorded on an excel spread sheet then statistically analysed by a blinded assessor ([name] - A member of the study management team, but directly not involved in patient recruitment). The same individual, who will not be involved in patient recruitment, will take all the measurements. Measurements will be taken using a standard 20cm ruler with 1mm increments and recorded to the nearest. Incomplete patient assessment records will be included on an intention to treat basis. A summary of the investigations, treatment and assessment can be found in Appendix 5. A planned time for the SToICAL study is outline in a Chart (Appendix 6)

Patient recruitment process during outpatient clinic:

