7.2 THE NUMBER OF PARTICIPANTS

Minimally clinical important difference of 20mm will be used as the clinically admissible margin of non-inferiority. From previous studies, it is assumed to use a standard deviation of 25mm and with a 95% power calculations have determined a required sample size of 41 per study arm, when including a 20% fall out rate a total sample size of 100 patients will be required²².

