7.4 RANDOMISATION

Patients will be randomised using the simple randomisation service provided by Sealed Envelope Ltd (<https://www.sealedenvelope.com>). This is an online service that provides random permuted block randomisation, ensuring participants are balanced between the control and treatment group.

7.5 CRITERIA FOR THE TERMINATION OF THE TRIAL.

Once 100 patients have been recruited and randomised to the trial.

7.6 PROCEDURE FOR ACCOUNTING FOR MISSING, UNUSED, AND SPURIOUS DATA.

A 20% fall out rate has been considered. Participants who have not returned their patient assessment records will not be included in the analysis. Results from partially completed forms will be included for analysis.

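### Nothing in the body text shows that a 1-hour VAS was marked at 1 hour, and the call after 24 hours can prompt a missed line to be filled in from memory

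*Combined protocol and SAP*

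**What the plan says.** Section 7.1 makes the change in VAS from pre-injection to 1 hour the primary outcome. Under section 3 the pre-injection, injection and 5-minute scores are marked in clinic. The 1-, 2-, 3- and 24-hour scores are marked by the patient, on paper, after leaving.

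On timing, section 3 states: "The timings at which these scores must be recorded will be clearly documented on the patient assessment record by the physician before leaving clinic". These are the times at which scores are due. The only time that the body text shows the patient entering is when any painkiller was taken.

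The one contact after clinic comes after the 24-hour score: a "follow-up call by the registrar to ensure the assessment form has been completed". The same call answers questions and reminds the patient to post the form. Returned forms stay sealed until recruitment ends.

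On data handling, section 7.6 says "Results from partially completed forms will be included for analysis". Section 7.7 includes everyone randomised who returned a form. Neither section has a rule for a line marked late or from memory. On the drug, section 1.1 says of lidocaine that "its effects can last for 1 to 3 hours"; section 1.2 gives 2 to 3 hours.

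**The concern.** The hypothesis is tied to one time point inside a short pharmacological window, and the plan describes no means of confirming that a score labelled 1-hour was given at 1 hour. A patient who missed the line is asked about completeness about 23 hours later (24 − 1). Neither patient nor caller is told to leave a missed line blank, and section 6 ties the end of participation to having completed every score. The natural response is to fill the gap from memory, and the result cannot be told apart from a timely mark.

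By 3 hours the anaesthetic effect is ending on the protocol's own figures, and by 24 hours it has gone. A mark coloured by pain at those times may have lost the contrast that the trial is meant to measure. In a superiority trial such dilution would be conservative. Here it works towards the hypothesis that corticosteroid alone is no worse.

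**Working it through.** **Inputs from the plan**
- Margin 20 mm: "Minimally clinical important difference of 20mm will be used as the clinically admissible margin of non-inferiority" (section 7.2).
- SD 25 mm: "it is assumed to use a standard deviation of 25mm" (section 7.2).
- Size: "95% power calculations have determined a required sample size of 41 per study arm", and "when including a 20% fall out rate a total sample size of 100 patients will be required" (section 7.2).
- Two-sided 5% with 95% confidence intervals (section 7.3), taken here as one-sided 2.5% for non-inferiority.
- Two balanced arms (section 7.4), taken as 1:1.

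**Inputs that the plan does not give (assumptions)**
- Share f of 1-hour scores marked late: 0 to 50%.
- Arm difference d carried by those late scores: −10 to +30 mm when the true 1-hour difference is 20 mm.
- SD held at 25 mm unless stated.
- Non-inferiority is declared when the upper 95% limit of the difference (corticosteroid alone minus combination) is below 20 mm.

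**The plan's own figure**

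n per arm = 2 × (1.960 + 1.645)² × 25² / 20² = 2 × 12.996 × 1.5625 = 40.6, so 41. Power at 41 per arm is 95.2%. For the total, 82 / 0.8 = 102.5 and 82 × 1.2 = 98.4, so the stated 100 lies between the two usual ways of adding 20%. The figures reproduce.

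**Effect of late marks**

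SE = 25 × √(2/41) = 5.52 mm.

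Expected observed difference = (1 − f) × D + f × d, where D is the true 1-hour difference.

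Chance of declaring non-inferiority = Φ((20 − expected difference)/SE − 1.96).

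With d = 0 (late marks carry no arm difference):

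| Late marks f | D = 20: expected difference | Chance of declaring | D = 25: expected difference | Chance of declaring |
|---|---|---|---|---|
| 0% | 20 mm | 2.5% | 25 mm | 0.2% |
| 10% | 18 mm | 5.5% | 22.5 mm | 0.8% |
| 20% | 16 mm | 10.8% | 20 mm | 2.5% |
| 30% | 14 mm | 19.1% | 17.5 mm | 6.6% |
| 50% | 10 mm | 44.1% | 12.5 mm | 27.4% |

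For D = 20 and f = 20%: (20 − 16)/5.52 − 1.96 = 0.72 − 1.96 = −1.24, and Φ(−1.24) is about 10.8%.

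**Other kinds of recall error (D = 20)**

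| d, difference carried by late marks | f = 20% | f = 30% |
|---|---|---|
| −10 mm | 19.1% | 37.1% |
| 0 mm | 10.8% | 19.1% |
| +10 mm | 5.5% | 7.8% |
| +20 mm (unbiased) | 2.5% | 2.5% |
| +30 mm (exaggerated) | 1.0% | 0.6% |

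**Noise only.** If late marks are unbiased but add an independent error with SD 25 mm, the overall SD becomes √(625 + f × 625), which is 27.4 mm at f = 20% and 28.5 mm at f = 30%. The error rate stays at 2.5%. Power at a true difference of zero falls from 95.2% to 91.1% and 88.8%.

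**The case against.** The strongest reply is that much of this is inference.

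- **The form is not shown.** Appendix 4 may already have a box for completion time. This stands: one can say only that the body text describes none. A time box would still leave the call without an instruction and section 7.6 without a timing rule.
- **There is a safeguard, and blanks are allowed.** Due times are written on the form before the patient leaves, partial forms are accepted, and no text asks for missed scores to be filled in. This also stands. The call can prompt back-filling; the plan does not direct it.
- **Direction is not fixed.** A reader might infer that late marks must pull the arms together and favour non-inferiority. The documents do not support that as a certainty. A line marked at 90 minutes or 2 hours may still fall within the stated lidocaine effect. Unbiased recall only costs power, and exaggerated recall works against non-inferiority.
- **Size is easily overread.** A reader might infer that diluting a true 25 mm down to the 20 mm margin rescues an inferior treatment. At the margin it still passes only 2.5% of the time; it takes 30% late marks to reach about 7% and 50% to reach about 27%.
- **The caller's knowledge of the arm.** A registrar prepares the injection and a registrar makes the call, so a reader might infer that the caller knows the allocation. The text does not say that they are the same person, nor that the caller hears or records scores.
- **Self-entered times can be copied from the due times.** True. They reduce undetected back-filling but cannot exclude it.

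**Conclusion.** The point holds in a limited form and is worth correcting. As described, the plan cannot confirm that a 1-hour score was marked at 1 hour. Its only later contact can prompt completion from memory, and no rule covers such scores. Dilution towards non-inferiority is plausible given the short lidocaine effect, but it is conditional.

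If late marks carry no arm difference, with a true difference of 20 mm, SD 25 mm and 41 per arm, false non-inferiority rises from 2.5% to about 11% at 20% late marks and 19% at 30%. Across the recall errors considered, the rate at 20% late marks runs from 1.0% to 19.1%. The documents give neither the share of late marks nor the difference they carry, so these figures illustrate sensitivity and do not predict bias. If actual times are not captured during the trial, the analysis cannot separate these possibilities afterwards.

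**What to change.** 1. **Section 3, follow-up call.** State that the call reminds the patient to return the form and answers questions, and that the caller must not ask for missed earlier scores to be filled in. Missed lines stay blank.
2. **Patient assessment record.** Unless the form already has one, add a box beside each home VAS line for the actual time at which it was marked.
3. **Section 7.6.** Keep all returned 1-hour scores in the primary analysis, consistent with the inclusion rule in section 7.7. Pre-specify a sensitivity analysis restricted to 1-hour scores marked within a window that the sponsor fixes before the sealed forms are opened.

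The cost is one extra field, one instruction to the caller and one additional analysis. A few more 1-hour scores may be missing because they are no longer prompted. No visits or patients are added. Because self-entered times can be copied or guessed, the sensitivity analysis limits the problem and does not remove it.
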